9.8 Multiplicity

Multiplicity for the Phase 2 Cohort and the Phase 3 Cohort will be considered separately in this operationally seamless adaptive design study.

Phase 2 Cohort

For the Phase 2 Cohort Base Period, there are 3 treatment group comparisons that may be tested to address the primary hypothesis. Testing will be done in a sequential manner in descending order of MK-5475 randomized dose group, stopping at the point statistical significance is not achieved.

The multiplicity strategy strongly controls the Type I error at 2.5% (one-sided) to address the primary hypothesis.

Phase 3 Cohort

As there is a single hypothesis involving a single comparison, no multiplicity control is required in the Phase 3 Cohort.

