9.4.2 Phase 3 Cohort Efficacy Endpoints

Primary Efficacy Endpoint

• Mean change from baseline in 6MWD at Week 12

Secondary Efficacy Endpoint

- Mean change from baseline in 6MWD at Week 24
- Proportion of participants whose WHO-FC is not worse at Week 12 relative to baseline

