9.6 Statistical Methods

Statistical testing and inference for safety analyses are described in Section 9.6.2. Efficacy results that will be deemed to be statistically significant after consideration of the Type I error control strategy are described in Section 9.8. Nominal *p*-values for secondary endpoints may be provided as an assessment of strength of evidence without intent to make inferential claims. All statistical tests will be conducted at the α =0.025 (one-sided) level.

For analysis purposes, the baseline assessment is considered the one closest to but before or on the day of randomization (Day 1).

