Through 12 weeks post-randomization, drop-out is expected to be approximately 10% in each treatment group. However, based on the approach to missing data, all randomized participants per group are expected to be included in the primary analysis and are the basis for sample size and power calculations, accounting for imputation of missing data.

Power and sample size are based on the change from baseline in 6MWD at Week 12. Assuming the true change from baseline in 6MWD at Week 12 is 30 meters for MK-5475 versus 0 meters for placebo, the assumed change from baseline in 6MWD at Week 12 using J2R to impute missing data would be 27 meters for MK-5475 versus 0 meters for placebo. The assumed standard deviation of the difference of change from baseline in 6MWD at Week 12 between each MK-5475 and placebo is 70 meters. Under these assumed change and standard deviation, a sample size of 143/group provides 90% power to demonstrate superiority for each of the MK-5475 treatment comparisons using a one-sided alpha=0.025.

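### As written, Phase 3 cannot reach an error-controlled conclusion on 6MWD at Week 24, although a test gated behind the Week 12 primary would cost no alpha, power or participants

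*Combined protocol and SAP*

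**What the plan says.** Section 3 gives the Phase 3 Cohort one hypothesis, superiority on 6MWD at Week 12. It also lists the effect on 6MWD at Week 24 as a secondary objective, but without a hypothesis. Section 9.4.2 names the matching endpoint, "Mean change from baseline in 6MWD at Week 24", alongside a Week 12 WHO-FC proportion.

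Four places settle how far Week 24 6MWD can be used:

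- Section 9.1 (Phase 3 table) lists key secondary endpoints as N/A.
- Section 9.6 says that nominal p-values "for secondary endpoints may be provided as an assessment of strength of evidence without intent to make inferential claims".
- Section 9.6.1 rules out statistical comparisons in either Extension Period. Section 9.6.1.2 makes Week 24 the Phase 3 Extension timepoint.
- Section 9.8 reads: "As there is a single hypothesis involving a single comparison, no multiplicity control is required in the Phase 3 Cohort".

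Against this, Section 9.6.1.2 and Table 6 analyse Week 24 6MWD by robust regression with jump-to-reference (J2R) imputation. That model exists to estimate a treatment difference. WHO-FC receives summary statistics only.

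**The concern.** Phase 3 is the confirmatory cohort, and the Week 24 data suit a controlled comparison. Section 4.1 keeps the Extension Period double-blind and placebo-controlled. Section 8.2.2 schedules the walk test at every Phase 3 site visit, and Section 8.11.5 keeps it for participants who stop study treatment. The plan would thus collect, blind and model this comparison, yet could report it only as supportive.

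What is at stake is whether the trial can answer its own Week 24 objective with controlled error. The primary test is not affected. The text also has to be repaired in any case, because Section 9.6.1 forbids a comparison that Table 6 prescribes.

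**Working it through.** **Inputs from the documents**

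- Alpha (Section 9.6): "All statistical tests will be conducted at the α =0.025 (one-sided) level".
- Size and power (Section 9.9.1): "a sample size of 143/group provides 90% power to demonstrate superiority".
- Effect (Section 9.9.1): 30 m before imputation; "using J2R to impute missing data would be 27 meters for MK-5475 versus 0 meters for placebo".
- Dropout (Section 9.9.1): "drop-out is expected to be approximately 10% in each treatment group", stated through Week 12. Hence 30 × (1 − 0.10) = 27 m.
- SD (Section 9.9.1): "between each MK-5475 and placebo is 70 meters". It is read here as the SD of one participant's change, the reading that reproduces the plan's power.

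**Step 1: the plan's own figure**

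SE = 70 × √(2/143) = 8.278 m. Noncentrality = 27/8.278 = 3.26. Power = Φ(3.26 − 1.96) = 90.3% (noncentral t: 90.2%). The sample size formula gives 142 per group, against 143 stated. The 90% is reproduced.

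**Step 2: what a gate does to error and to the primary**

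Rule: test Week 24 at one-sided 0.025 only if Week 12 is significant at one-sided 0.025.

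- If both nulls are true, any rejection first requires a false rejection at Week 12, so familywise error is 0.025.
- If only the Week 12 null is true, the only possible error is that rejection, again 0.025.
- If only the Week 24 null is true, error is at most 0.025 (computed 0.0249 to 0.0250 for correlations of 0.5 to 0.9).
- The primary is tested first at full alpha, so its power (90.3%) and N (286) do not change.

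For comparison, splitting alpha to 0.0125 each would cut primary power to 84.6%. Claiming Week 24 at 0.025 with no gate would give a familywise error under the global null of 0.05 − P(both reject): 4.9% at correlation 0 and 3.5% at correlation 0.9. The plan makes no such claim.

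**Step 3: what the gated test could deliver**

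The documents give no Week 24 effect, SD, dropout or Week 12 to Week 24 correlation. Assumptions: SD 70 m; underlying effect still 30 m; missing share m, giving 30 × (1 − m) after J2R; bivariate normal test statistics with correlation 0.5 to 0.9. Power to win both is P(Z12 > 1.96 and Z24 > 1.96), with means 3.26 and 30 × (1 − m)/8.278.

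| m at Week 24 | Effect after J2R | Week 24 test alone | Both tests, correlation 0.5 | 0.7 | 0.9 |
|---|---|---|---|---|---|
| 10% | 27 m | 90.3% | 0.8378 | 0.8517 | 0.8731 |
| 20% | 24 m | 82.6% | 0.7755 | 0.7923 | 0.8150 |
| 30% | 21 m | 71.8% | 0.6827 | 0.6992 | 0.7154 |

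The first row assumes no loss beyond the dropout planned to Week 12, so it is a best case. The lower rows can also be read as a smaller underlying effect.

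**The case against.** The strongest reply is that this is a disclosed choice. With one hypothesis, the sentence in Section 9.8 is right, and Section 9.6 openly makes secondary p-values nominal. A sponsor may keep its secondaries supportive. This stands. A reader might infer that Phase 3 inflates Type I error by testing secondaries outside a procedure; the documents do not support that, because no inferential claim is attached to them.

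A reader might also infer that the trial can never conclude anything formal about Week 24. That goes too far: Section 9 allows key secondary hypotheses to be changed by protocol amendment before any unblinding. Nor is this a point about secondary endpoints in general. WHO-FC has no test and no hypothesis, and nothing here requires one.

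It may further be said that longer-term benefit is pursued another way. Under Section 4.1, Phase 3 treatment continues until enough clinical worsening events accrue across this cohort and a second study, under a separate integrated analysis plan. That is fair, and the documents do not show that a 12-week conclusion is inadequate. But clinical worsening is a different question from the Week 24 walk-distance objective that this protocol sets itself.

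Two practical objections also stand, and they shape the fix. Changing Section 9.8 alone would contradict Section 9.6.1. And Section 9.2 plans Phase 3 database locks only at the end of the Base Period and at the end of an Extension Period of up to 5 years, so a formal Week 24 test needs a stated cutoff.

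**Conclusion.** The point holds as a missed improvement that costs the primary nothing, limited to 6MWD at Week 24. It is not an error in the multiplicity statement. As written, Sections 9.1, 9.6, 9.6.1 and 9.8 together prevent an error-controlled Week 24 conclusion, and Section 9.6.1 conflicts with Section 9.6.1.2 and Table 6.

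The error-control result rests only on the order of testing and on each test being valid at its level. The chance of winning both tests, between about 68% and 87% across the cases shown, rests on an assumed Week 24 effect, SD, missing share and correlation. It also uses a normal approximation to the planned robust regression. It measures what the added test could deliver, not harm done by the present plan.

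**What to change.** Amend before the Phase 3 Base Period is unblinded. Sections 9.2 and 9.7 let the study team see the Week 12 results before the Extension analysis, and a rule added after that would not be credible as prespecified.

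1. Section 3 (and the synopsis): add a superiority hypothesis for change in 6MWD at Week 24.
2. Section 9.1: name it the Phase 3 key secondary endpoint.
3. Section 9.8: test it at one-sided 0.025 only if Week 12 6MWD is significant at one-sided 0.025; otherwise treat it as descriptive.
4. Sections 9.6 and 9.6.1: exempt this one comparison from the nominal-only sentence and from the bar on Extension Period comparisons. This also resolves the conflict with Table 6.
5. Section 9.6.1.2: use the Phase 3 primary's imputation model. The Week 24 analysis now refers to Section 9.6.1.1, where imputation uses an ANCOVA, whereas the Phase 3 primary imputes from an MMRM.
6. Section 9.2: state one data cutoff, either a Week 24 cut or the Extension Period lock, so that the test is done once.

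The cost is text in these sections and, if a Week 24 cut is chosen, one extra data cut with its blinding arrangements. Choosing the Extension lock avoids that but delays the answer until the Extension ends. No alpha, primary power, participants or visits are spent.

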9.9 Sample Size and Power Calculations

Sample size and power calculations for the Phase 2 Cohort and the Phase 3 Cohort have been performed separately in this operationally seamless adaptive design study.

9.9.1 Efficacy

Phase 2 Cohort

08P53K

The study design assumptions are based on results from other Phase 2 clinical trials in the literature for PAH participants with similar design. In the Phase 2 study assessing selexipag, the observed mean percent change from baseline PVR was 33% with standard deviation 0.34,

and the overall study completion rate was 91% [Simonneau, G., et al 2012]. Comparable results were reported in a Phase 2 study assessing riociguat [Ghofrani, H. A., et al 2010].

Through 12 weeks post-randomization, drop-out is expected to be approximately 10% in each treatment group. However, based on the approach to missing data, all randomized participants per group are expected to be included in the primary analysis and are the basis for sample size and power calculations, accounting for imputation of missing data.

Power and sample size are based on the percent change from baseline in PVR at Week 12. Assuming the true percent change from baseline in PVR at Week 12 is -30% for each MK-5475 dose versus 0% for placebo, the assumed percent change from baseline in PVR at Week 12 using J2R to impute missing data would be 27% for each MK-5475 dose versus 0% for placebo. The assumed standard deviation of the difference of percent change from baseline in PVR at Week 12 between each MK-5475 and placebo is 0.4. Under these assumed percent change and standard deviation, a sample size of 41/group provides more than 85% power (approximately 86.4%) to demonstrate superiority for each of the MK-5475 treatment comparisons using a one-sided alpha=0.025.

With respect to the secondary endpoint of change from baseline in 6MWD at Week 12, a sample size of 41/group will provide a half-width of the 95% CI to be 30 meters, assuming the standard deviation of the change from baseline in 6MWD is 70.

Phase 3 Cohort

The study design assumptions are based on results from Phase 3 PAH clinical studies in the literature with similar design [Ghofrani, H. A., et al 2013] [Galie, N., et al 2008] [Galie, N., et al 2005] [Rubin, L. J., et al 2002]. A clinically relevant increase in 6MWD (>30 meters) correlates with improved clinical outcomes in PAH (Section 4.2.1.1).

Through 12 weeks post-randomization, drop-out is expected to be approximately 10% in each treatment group. However, based on the approach to missing data, all randomized participants per group are expected to be included in the primary analysis and are the basis for sample size and power calculations, accounting for imputation of missing data.

Power and sample size are based on the change from baseline in 6MWD at Week 12. Assuming the true change from baseline in 6MWD at Week 12 is 30 meters for MK-5475 versus 0 meters for placebo, the assumed change from baseline in 6MWD at Week 12 using J2R to impute missing data would be 27 meters for MK-5475 versus 0 meters for placebo. The assumed standard deviation of the difference of change from baseline in 6MWD at Week 12 between each MK-5475 and placebo is 70 meters. Under these assumed change and standard deviation, a sample size of 143/group provides 90% power to demonstrate superiority for each of the MK-5475 treatment comparisons using a one-sided alpha=0.025.

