At Visit 2, participants who meet study eligibility criteria will enter the double-blind treatment period, as described below for each cohort.

Phase 2 Cohort

In the Phase 2 Cohort Base Period, 3 doses of MK-5475 ($380 \ \mu g$, $100 \ \mu g$, and $32 \ \mu g$) will be compared to placebo. The efficacy, safety, and tolerability of each MK-5475 dose will be assessed when all participants in the Phase 2 Cohort Base Period have completed or discontinued the 12-week treatment period. An IA for efficacy and futility (nonbinding) is

planned when approximately 120 participants have completed or discontinued the Phase 2 Cohort Base Period. The Phase 2 Cohort Base Period may stop at the IA and a dose for the Phase 3 Cohort may be selected at that time OR the study may be stopped early for futility (Section 9.7).

The primary objective of the Phase 2 Cohort Base Period is to evaluate the effect of MK-5475 versus placebo on PVR in participants with PAH at Week 12. Of the 3 MK-5475 doses studied, the dose (380 μ g, 100 μ g, or 32 μ g) with the best efficacy and safety profile in the Base Period of this cohort will be selected for evaluation in the subsequent Phase 3 confirmatory cohort, alongside a placebo control group.

Participants who remain on study intervention and complete the Visit 6/Week 12 assessments (*including RHC*) may enroll in the ~40-month blinded Extension Period if they satisfy the SpO₂ and seated BP study eligibility criteria (Section 5.2) at Week 12 and provide documented informed consent. Participants who discontinue study intervention or complete the Phase 2 Cohort Base Period before Amendment 01 is approved and the Extension Period becomes available will not be eligible to enroll in the Extension Period.

The objective of the Phase 2 Cohort Extension Period is to evaluate the longer-term safety and tolerability of the 3 doses of MK-5475 (380 μ g, 100 μ g, or 32 μ g) in this participant population.

To supplement the routine blinded trial monitoring outlined in this study, an external DMC will monitor the interim data (Section 9.7).

This Phase 2/3 study may be stopped if analysis of the data collected either at the time of the IA or at the end of the Phase 2 Cohort Base Period shows that none of the MK-5475 doses has a desirable efficacy and safety profile.

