Based on all the considerations, the top dose selected for the Phase 2 Cohort of this study is 380 μ g. A low dose of 32 μ g is selected for evaluation in the Phase 2 Cohort, to expand the exposure-response dataset that can be used to inform dose selection for the Phase 3 Cohort and for future studies and to define a minimally efficacious dose. The 32 μ g inhaler formulated for the Phase 2/3 study is the lowest feasible strength that can be developed using a conventional formulation. The mid dose of 100 μ g is selected for evaluation in the Phase 2 Cohort based on minimal overlap of plasma exposures from that at the high dose at 380 μ g and the low dose at 32 μ g.

Participant response to the 3 different doses of MK-5475 ($32 \mu g$, $100 \mu g$, and $380 \mu g$) will be assessed in the Phase 2 Cohort Base Period. Of these, the treatment dose that shows the best efficacy, as assessed by pulmonary vascular hemodynamics, no evidence of clinically meaningful systemic hypotension, and overall favorable safety profile will be selected for the subsequent Phase 3 Cohort.

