9.1 Statistical Analysis Plan Summary

Key elements of the statistical analysis plan are summarized below; the comprehensive plan is provided in Sections 9.2 through 9.12.

Study Design Overview		
Treatment Assignment	Base Period: Participants (approximately 41/group) will be randomized in a 1:1:1:1 ratio among 4 treatment groups: 1) MK-5475 380 µg	
	2) MK-5475 100 μg	
	3) MK-5475 32 μg	
	4) placebo matching MK-5475	
	 Extension Period: Participants in the 3 active treatment groups in the Base Period will initially maintain the same treatment assignment in the Extension Period; participants who received placebo during the Base Period will initially be randomized in a 1:1:1 ratio among the 3 treatment groups: 1) MK-5475 380 μg 	
	2) MK-5475 100 μg	
	3) MK-5475 32 μg	
	After the Phase 3 dose is selected, all participants in the Phase 2 Cohort Extension will receive the selected Phase 3 dose regardless of their randomized treatment group.	
Analysis Populations	Efficacy: FAS	
	Safety: APaT	

Phase 2 Cohort

Primary Endpoint	Percent Change from baseline in PVR at Week 12		
Key Secondary Endpoints	N/A		
Statistical Methods for Key Efficacy Analyses	The differences (each MK-5475 dose minus placebo) in percent change from baseline and the associated 95% CIs and p -values will be provided based on a robust regression model. Missing PVR observations at Week 12 from participants in all treatment groups will be imputed based on the observed PVR observations at Week 12 from the placebo group.		
Statistical Methods for Key Safety Analyses	For analyses in which 95% CIs will be provided for between- treatment differences (each MK-5475 dose minus placebo) in the percentage of participants with events, these analyses will be performed using the M&N method.		
Interim Analyses	One interim analysis is planned when Complete or discontinued the Phase 2 Cohort Base Period. The purpose of the IA is to allow an early stop for Phase 2 Cohort Base Period for efficacy (including selection of the Phase 3 dose) or to stop the study for futility. Results will be reviewed by an eDMC. The primary analysis of efficacy data from the Phase 2 Cohort will occur when all participants in this cohort have completed (or discontinued prior to the end of) the Base Period. Although the Phase 2 Cohort can continue in the study (in the Extension Period), the Base Period analysis is not considered an interim analysis.		

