Multiplicity	There are 3 treatment group comparisons that may be tested to address the primary hypothesis. Testing will be done in a sequential manner in descending order of MK-5475 randomized dose group, stopping at the point statistical significance is not achieved.		
Sample Size and Power	The planned sample size is approximately 164 participants. For the percent change from baseline in PVR at Week 12, the study has 85% power to demonstrate that MK-5475 380 μ g is superior to placebo group at an overall one-sided 2.5% alpha level.		

Phase 3 Cohort

Study Design Overview			
Treatment Assignment	 Participants (approximately 143/group) will be randomized in a 1:1 ratio between 2 treatment groups: 1) MK-5475 2) placebo matching MK-5475 		
Analysis Populations	Efficacy: FAS Safety: APaT		
Primary Endpoint	Change from baseline in 6MWD at Week 12		
Key Secondary Endpoints	N/A		
Statistical Methods for Key Efficacy Analyses	The difference (MK-5475 minus placebo) in change from baseline and the associated 95% CI and p -value will be provided based on a robust regression model. Missing 6MWD observations at Week 12 from participants in both treatment groups will be imputed based on the observed 6MWD observations at Week 12 from the placebo group.		
Statistical Methods for Key Safety Analyses	For analyses in which 95% CIs will be provided for between- treatment differences (MK-5475 minus placebo) in the percentage of participants with events, these analyses will be performed using the M&N method.		
Interim Analyses	No interim analyses are planned. (The primary analysis of efficacy data from the Phase 3 Cohort will occur when all participants in this cohort have completed [or discontinued prior to the end of] the Base Period. Although the Phase 3 Cohort will continue in the study [in the Extension Period], the Base Period analysis is not considered an interim analysis.)		
Multiplicity	As there is a single hypothesis test involving a single endpoint and a single between-treatment comparison, no multiplicity adjustment is required.		
Sample Size and Power	The planned sample size is approximately 286 participants. For the change from baseline in 6MWD at Week 12, the study has 90% power to demonstrate that MK-5475 is superior to placebo group at a one-sided 2.5% alpha level.		

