9.7 Interim Analyses

Analyses of data to be performed while the study is in progress are described below.

The O'Brien–Fleming alpha-spending function [Lan, K. K. G. and DeMets, D. L. 1983] will be used for the efficacy IA to assess the superiority of MK-5475 versus placebo. The spending function can be expressed as

$$\alpha(t) = 2 - 2\Phi\left(\frac{Z_{\alpha/2}}{\sqrt{t}}\right)$$

where 't' denotes the percentage of information included at the IA, and ' Φ ' denotes the standard normal cumulative distribution function.

[figure not shown]
With this alpha spending approach, the cumulative significance level will be approximately (one-sided) at the IA and **Control** at the final analysis of the Phase 2 Cohort Base Period, respectively. This testing approach controls the one-sided alpha between the efficacy IA and final analysis at 0.025. The operating characteristics for the interim efficacy analysis are shown in Table 8.

Table 8Power to Demonstrate Superiority of MK-5475 vs placebo on the Primary
Endpoint of % Change in PVR in Phase 2 Cohort Base Period at the Interim Analysis

Analysis timepoint	Cumulative a Spent	Pow	er (%) foi	· Various]	Frue Effect	t Sizes
	(one-sided)	-30%	-35%	-40%	-45%	-50%
	CCI	59.5	75.0	86.7	93.9	97.6

IA=interim analysis; PVR=pulmonary vascular resistance.

Study enrollment will not be paused while the IA is being conducted. Blinding to treatment assignment will be maintained at all investigational sites. Participant-level unblinding will be restricted to an internal unblinded statistician and a scientific programmer performing the IA. Treatment-level results and/or participant-level data from the IA will be provided by the unblinded statistician to the eDMC. Limited additional Sponsor personnel may be unblinded to the treatment-level results of the IA, if required, to act on the recommendations of the eDMC. The processes by which recommendations and decisions are reached and communicated will be documented in the DMC charter. Before final study unblinding, individuals who have been unblinded at any level will not be involved in any discussions regarding modifications to the protocol, statistical methods, identification of protocol deviations, or data validation efforts after the IA. The results of the IA will not be shared with the investigators before completion of the Phase 2 Cohort.

Phase 2 Cohort Base Period

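### The 86.4% power in Section 9.9.1 is single-look, ungated power; under Sections 9.7 and 9.8 power is about 65–77% for 100 µg and 53–71% for 32 µg

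*Combined protocol and SAP*

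**What the plan says.** Section 9.9.1 (Phase 2) assumes a 30% true reduction in PVR for every dose. This becomes 27% after jump-to-reference imputation with 10% drop-out, against 0% on placebo, with an SD of 0.4. It concludes that "a sample size of 41/group provides more than 85% power (approximately 86.4%) to demonstrate superiority for each of the MK-5475 treatment comparisons" at one-sided 0.025. It mentions neither the testing order nor the interim analysis.

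Section 9.8 sets the testing order: "Testing will be done in a sequential manner in descending order of MK-5475 randomized dose group", ending at the first non-significant result.

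On the interim, Section 4.1 places it at about 120 participants and says "The Phase 2 Cohort Base Period may stop at the IA". Section 9.1 adds "The purpose of the IA is to allow an early stop for Phase 2 Cohort Base Period for efficacy". Section 9.7 gives an O'Brien–Fleming-type spending function and notes "Study enrollment will not be paused while the IA is being conducted".

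Section 9.1 makes a narrower power claim: 85% for 380 µg alone, to show it "superior to placebo group at an overall one-sided 2.5% alpha level".

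On thresholds, Section 9.6 states "All statistical tests will be conducted at the α =0.025 (one-sided) level". Section 9.6.1.1 declares significance at a one-sided p-value below 0.025, subject only to Section 9.8.

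Section 4.3 gives the reasons for including 32 µg: to inform dose choice for Phase 3 and "for future studies and to define a minimally efficacious dose".

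**The concern.** Under Section 9.8, 100 µg can be declared superior only if 380 µg is, and 32 µg only if both higher doses are. When the true effects are equal, as Section 9.9.1 assumes, the three comparisons cannot all have the same power. How far power falls for the lower doses also depends on what happens to them if 380 µg crosses at the interim, and the readable text does not say.

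A reader of Section 9.9.1 would put the chance of missing a true effect at 32 µg at about 14% (100 − 86.4). If the real chance is two to three times that, a non-significant result at 32 µg could be over-read as absence of effect, at the dose meant to help define the lowest effective one.

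A second, smaller matter is that the 0.025 threshold in Sections 9.6 and 9.6.1.1 carries no reference to the interim boundary. Used as written at the final analysis, it would spend slightly more than the intended 0.025.

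**Working it through.** **Inputs.** Effect 0.27, SD 0.4 (the plan's figure reproduces when this is used as the per-arm SD), 41 per group and one-sided alpha 0.025 come from Section 9.9.1. The fixed sequence is from Section 9.8, the interim at about 120 of 164 (30 per group) from Section 4.1, and the spending function from Section 9.7. The shared placebo arm gives a correlation of 0.5 between comparisons. True effects are equal, and the nonbinding futility stop is ignored.

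**1. The plan's figure.** θ = 0.27 / (0.4 × √(2/41)) = 3.056. Power = Φ(3.056 − 1.960) = 86.35%, which matches the stated 86.4%.

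**2. Fixed sequence, one look.** The multivariate normal probability that the first two comparisons both succeed is 77.7%; that all three succeed, 71.6%.

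**3. Interim boundary.** At t = 120/164 = 0.732 the printed spending function gives a cumulative alpha of 0.00879 (z = 2.375). With 30 per group and effects multiplied by 0.9, interim power for true effects of 30, 35, 40, 45 and 50% is 59.5, 75.0, 86.7, 93.9 and 97.6%. These match all five values in Table 8, which supports the model although the plan's own alpha levels are blacked out. Solving the bivariate normal for an overall 0.025 gives a final z of 2.007 (p = 0.0224).

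**4. Power with both features.** The 380 µg figure is exact (bivariate normal). The others come from 4,000,000 simulated four-arm trials per setting.

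| Interim at about 120 of 164 | 380 µg | 100 µg | 32 µg |
|---|---|---|---|
| As stated in 9.9.1 | 86.4% | 86.4% | 86.4% |
| Fixed sequence, no interim | 86.4% | 77.7% | 71.6% |
| Interim, all doses tested at both looks | 85.8% | 76.9% | 70.6% |
| Interim, testing ends when 380 µg crosses | 85.8% | 65.1% | 53.2% |

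In the last row, 100 and 32 µg are tested only at the interim boundary if 380 µg crosses there (probability 59.5%); otherwise all doses are tested at the final boundary.

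**5. Sensitivity.** For 380/100/32 µg:

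- Interim at 110: 85.9/77.1/70.8% without stopping, 85.9/63.8/51.6% with stopping.
- Interim at 130: 85.7/76.7/70.4% without stopping, 85.7/67.3/56.3% with stopping.

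Other rules fall inside the range for an interim at 120. Stopping only when both 380 and 100 µg cross gives 76.9% for 100 µg and 63.7% for 32 µg. Following all 164 and testing the lower doses at the final boundary gives 76.6% and 70.1%.

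**6. Chance that 32 µg is not declared superior.** As implied by Section 9.9.1: 100 − 86.4 = 13.6%. With the interim and no stopping: 100 − 70.6 = 29.4%. With stopping: 100 − 53.2 = 46.8%.

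**7. Literal 0.025 at the final analysis.** After an interim tested at z = 2.375, a final test at z = 1.960 gives a total one-sided error of 0.0274 per comparison (0.0268 with the interim at 110, 0.0280 at 130).

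**The case against.** The 86.4% is not a miscalculation. Power for each comparison at one-sided 0.025 can be read as a per-comparison figure, and Section 9.9.1 uses the same phrase for Phase 3, where there is only one comparison, so it may be template wording. The primary hypothesis needs only one superior dose, the 380 µg test decides it, and Section 9.1 already limits its claim to that dose. All of this stands, and it limits how much the point matters.

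The 65% and 53% rest on an assumed stopping rule. Parts of Section 9.7 are not visible, and a rule for the lower doses may be there. The enrolment statement in Section 9.7, and the statement in Section 9.1 that the primary analysis follows completion or discontinuation of all participants, give some support to the upper end. This is why a range is given. The shortfall itself does not depend on the assumption: the fixed sequence alone takes 32 µg from 86.4% to 71.6%.

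No readable dose-selection rule requires significance at 100 or 32 µg. Sections 4.2 and 4.3 rely on the whole efficacy and safety picture, and Section 9.7 allows MCP-Mod modelling. The risk is therefore one of interpretation.

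On the threshold, Section 9.7 says alpha is controlled at 0.025 across both looks, and Section 9.6 defers significance to the Type I error strategy. The intention is clear; only the cross-reference is missing.

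**Conclusion.** The concern holds. The plan's own testing procedure does not deliver the power that Section 9.9.1 states for 100 and 32 µg. With equal true effects and the interim at about 120 of 164, power is about 77% and 71% if all doses are tested at both looks, and about 65% and 53% if testing ends when 380 µg crosses. The chance of failing to declare 32 µg superior is about 29% to 47%, against the 14% implied. These figures rest on the plan's effect and SD, a shared placebo arm and no futility stop.

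The 380 µg power (85.8% with the interim, in line with Section 9.1), the power for at least one dose and the sample size stand. The threshold wording in Sections 9.6 and 9.6.1.1 is a cross-reference gap, worth about 0.0024 of one-sided alpha (0.0274 − 0.025) if read literally; it is not a failure of the intended control.

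**What to change.** In Section 9.9.1, label 86.4% as marginal (per-comparison, single-look) power, or limit it to 380 µg as Section 9.1 does. If power for the lower doses is stated, give the stopping assumption or both sets, for example:

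> Under Sections 9.7 and 9.8, with equal true effects and the interim at about 120 of 164 participants, power is about 86% for 380 µg. For 100 µg and 32 µg it is about 77% and 71% if all doses are tested at both looks, and about 65% and 53% if testing ends when 380 µg crosses at the interim.

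In Section 9.6, say that 0.025 is the overall one-sided level for Phase 2. In Section 9.6.1.1, declare significance against the boundary from the Section 9.7 spending function at the actual information fraction, contingent on Section 9.8, with 0.025 applying only if the interim is cancelled. As an illustration only, since the plan's levels are blacked out, the boundary at 120/164 is about 0.0088 at the interim and 0.0224 at the final analysis.

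The cost is wording only, with no change in sample size. The stated power for the two lower doses becomes less favourable, and the written final threshold becomes slightly stricter.
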